8.4. Statistical analysis set

All patients who met the inclusion and exclusion criteria were considered eligible for recruitment.

The two analysis sets in this study are defined as follows:

- The full analysis set (FAS) population analysis set will contain all eligible cases and shedding cases, but does not include culling cases.
- The Compliance (PP) population analysis set will include all subjects in the FAS analysis set with no significant deviation from the program.

Intention-to-treat and conformity analysis sets should be used to analyze the primary efficacy endpoints. The main analysis will be based on the PP analysis set. FAS analysis was regarded as supportive analysis.

9. Abbreviations

Abbreviations	Full Name	Chinese
AE	Adverse Event	不良事件
CFDA	China Food and Drug Administration	国家食品药品监督管理总局
CNDA	China National Drug Administration	国家食品药品监督管理总局
CRF	Clinical Record File	病例报告表
EUS	Ultrasound Endoscopy	超声内镜
CTCAE	Common Terminology Criteria for Adverse Events	不良事件常规评价标准
EC	Ethical Committee	伦理委员会
HBV	Hepatitis B Virus	乙型肝炎
ICD	Informed Consent Document	知情同意文件
ICF	Informed Consent Form	知情同意书
ITT	Intention To Treat	意向治疗分析集
PP	Per Protocol	符合方案集
SAE	Serious Adverse Event	严重不良事件

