6.3.4. Post-operative Managements

- 1) Routine postoperative care.
- 2) Subjects were observed until awakening.

- 3) Those without choledochal stones detected were followed up for 6 months (1st, 2nd, 3rd, and 6th months by telephone and instructed to review liver function and abdominal ultrasound).
- 4) Examination information, such as subject grouping, examining physician, examination time, sedation status, number of common bile duct stones found, and number of bile duct site scans, was recorded by the recorder.
- 5) Images, videos, and case data of the examination were collected.

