8.3. Sample Size Calculation

For the sample size determination, the level of bilateral significance was 5% ($\alpha=5\%$), 80% certainty ($\beta=20\%$), and based on previous reports of 90% diagnostic accuracy of endoscopists for common bile duct stones, a non-inferiority test of novice combined with AI non-inferiority to expert was performed, and a total of 147 patients were calculated to be enrolled. Assuming a 20% shedding rate, a total of 184 subjects were expected to be enrolled.

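### Section 8.4 has no rule for patients whose reference standard is incomplete; they are mainly EUS-negative, so a completers-only analysis raises sensitivity, lowers specificity and can shift accuracy

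*Combined protocol and SAP*

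**What the plan says.** Section 4.1 uses ERCP and 6-month follow-up as the reference standard. True and false positives are both settled at ERCP. A false negative is settled by a later ERCP or by a stone found during the 6 months, and a true negative by the 6-month result. (The true-negative definition appears to lack a 'not'; I read it as no stone found.)

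Section 6.3.4 limits follow-up to patients with a negative examination: "Those without choledochal stones detected were followed up for 6 months". The Study Process entry in section 1 describes the same telephone follow-up for patients without that limit.

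Section 8.3 gives the expected loss: "Assuming a 20% shedding rate, a total of 184 subjects were expected to be enrolled". The figure before inflation is 147.

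Section 8.4 makes PP the main analysis and FAS supportive. FAS is to "contain all eligible cases and shedding cases"; PP is FAS without significant deviations, a term that is not defined. Section 6.4 keeps data collected before a patient discontinues. Sections 7 and 7.5 let the expert's reading prevail when the two readers disagree.

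**The concern.** Whether a patient's true status becomes known depends on the EUS result. A positive reading leads to ERCP. A negative reading is usually resolved only if the patient stays in contact for 6 months. A patient read as negative who is lost, with no later ERCP, fits none of the four cells in section 4.1 and so cannot be scored in PP or in FAS. Dropping such patients is partial verification, and a complete-case analysis of it is biased in general.

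Missed stones lie among the negatives. Section 5.1 names fewer missed stones as an aim, and section 4.2 lists sensitivity and missed rates as secondary endpoints, so the distortion tends to flatter the figures behind that claim. The primary non-inferiority comparison of accuracy can move too.

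**Working it through.** **The plan's own figure.** 147/(1 − 0.20) = 183.75, rounded up to 184, which reproduces section 8.3. Expected loss is 184 − 147 = 37 (184 × 0.20 = 36.8).

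**Inputs.** N = 184 and 37 lost come from section 8.3. Accuracy of 0.90 comes from section 8.3 ("90% diagnostic accuracy of endoscopists for common bile duct stones"); I obtain it by assuming sensitivity (Se) = specificity (Sp) = 0.90. The documents give no trial prevalence, so it is an assumption. Section 2 mentions stones in 10-20% of symptomatic patients, and a predicted probability of 40-90% as the range where EUS is preferred.

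**Formulas, one reader.** Let L be the fraction of EUS-negatives lost at random. Then L = 37/(FN + TN), and among completers:

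- Se = TP/(TP + FN(1 − L))
- Sp = TN(1 − L)/(TN(1 − L) + FP)
- Accuracy = w·PPV + (1 − w)·NPV, where w is the share of completers read as positive

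Loss of negatives raises w. Accuracy therefore falls if NPV > PPV, is unchanged if they are equal, and rises otherwise.

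**Example at 10% prevalence.** TP 16.56, FN 1.84, TN 149.04, FP 16.56. L = 37/150.88 = 0.245, leaving FN 1.39 and TN 112.49. Se = 16.56/17.95 = 0.923; Sp = 112.49/129.05 = 0.872; accuracy = 129.05/147 = 0.878.

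**Range, all 37 losses EUS-negative (value before loss 0.900 throughout).**

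| Prevalence (assumed) | PPV | NPV | Se | Sp | Accuracy |
|---|---|---|---|---|---|
| 10% | 0.500 | 0.988 | 0.923 | 0.872 | 0.878 |
| 20% | 0.692 | 0.973 | 0.925 | 0.868 | 0.882 |
| 40% | 0.857 | 0.931 | 0.932 | 0.855 | 0.892 |
| 50% | 0.900 | 0.900 | 0.938 | 0.843 | 0.900 |
| 60% | 0.931 | 0.857 | 0.945 | 0.824 | 0.911 |

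**A less extreme case.** Take prevalence 10%, Se 0.80, Sp 0.925, so true accuracy is 0.9125. With 36.8 EUS-negatives lost, Se is 0.839, Sp 0.904 and accuracy 0.896. If half the loss occurs before EUS, 165.6 patients are examined and 18.4 negatives are then lost. Se is 0.821 and accuracy 0.904, a shift of 0.8 points.

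**Two readers.** Each patient has a novice and an expert reading, so the effect depends on whose negatives are lost.

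- *Loss among patients negative to both readers.* Both readers are right or both are wrong, so these patients contribute zero to the accuracy difference. Dropping 37 changes only the denominator and multiplies the difference by 184/147 = 1.25; a difference of −5.0 points becomes −6.3.
- *Loss among expert-negatives.* Assume novice Se = Sp = 0.85, expert 0.95, independent errors, prevalence 20% and 20% of expert-negatives lost. Novice positives fall from 53.4 to 48.9 and the novice's Se, Sp and accuracy stay at 0.850. The expert moves to Se 0.960 and Sp 0.938, and the difference goes from −10.0 to −9.3 points.
- *The same readers, with 20% of double-negatives lost instead.* Novice Se barely moves (0.850 to 0.851), novice Sp falls to 0.821, and the difference goes to −11.5 points. With independent errors few stones are missed by both readers, so the rise in sensitivity is small here.

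**Check of the remedy.** In the 10% example the weight for negatives is 150.88/(150.88 − 37) = 1.325. Then 1.39 × 1.325 = 1.84 and 112.49 × 1.325 = 149.04 (to rounding), the counts before loss.

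**The case against.** The strongest reply is that the plan never says lost patients leave the PP set. Loss to follow-up is not named as a significant deviation, FAS expressly keeps dropouts, and section 8.3 does not call the 147 completers. That is correct: exclusion is an inference. The gap remains, because an unverified negative cannot be scored in either set, and the data kept under section 6.4 lack the reference result. Counting lost negatives as true negatives would not repair it: with Se 0.80, Sp 0.925, prevalence 10% and 36.8 lost, sensitivity is still 0.839, and accuracy becomes 0.917 instead of 0.9125.

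A reader might also infer that no positives are ever lost. The documents do not support this. The expert prevails on disagreement, so a novice-positive, expert-negative patient may enter follow-up instead of ERCP and be lost, which removes a novice positive.

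Nor does every negative depend on completing 6 months. Section 4.1 accepts a later ERCP, and the contacts at months 1, 2 and 3 may reveal a stone early. Loss may then fall more on true negatives, which weakens the rise in sensitivity. Finally, sections 6.4.1 and 6.4.2 allow withdrawal before or during the procedure, so placing all 37 losses on negatives is an upper bound.

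**Conclusion.** The concern holds in this form: loss to follow-up falls mainly, not only, on patients read as negative, and section 8.4 does not say how they are scored. If they drop out, and loss is random among a reader's negatives, that reader's sensitivity is overstated and specificity understated. With Se = Sp = 0.90, the upper bound at 10% to 40% prevalence is about 2 to 3 points up on sensitivity, 3 to 4.5 points down on specificity and 1 to 2 points down on accuracy.

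It would be tempting to conclude that accuracy is always biased downward. It is not: under the same assumptions it is unchanged at 50% prevalence and rises to 0.911 at 60%. The effect on the paired difference has no fixed direction either. It can be magnified by up to 1.25 or can shift in the novice's favour.

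These sizes rest on assumed prevalence, reader performance and random loss. The point is modest and is best settled before analysis.

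**What to change.** In section 8.4, state how a patient without a completed reference standard is handled in PP and FAS, and make the following the analysis of accuracy, sensitivity, specificity and the paired accuracy difference:

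1. Include all randomised patients with both EUS readings. Patients with no reading have no pattern to weight; report their number separately.
2. Within each of the four novice-by-expert result patterns, weight verified patients by all/verified (Begg-Greenes), with a bootstrap confidence interval resampling patients.
3. Keep lost double-negatives in the denominator of the paired difference, where they contribute zero whatever their true status.
4. State the assumption that loss is random within pattern.
5. As sensitivity analyses, report the completers-only result and a range of assumed missed-stone rates among lost double-negatives. Counting all of them as missed stones is only an extreme bound: with Se 0.80, Sp 0.925, prevalence 10% and 36.8 lost, it would put sensitivity at 14.72/(14.72 + 2.82 + 36.8) = 0.27.

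The Study Process entry in section 1 and section 6.3.4 differ on who is followed up and must be reconciled.

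The cost is SAP wording and modest programming. The downside is the added assumption and a wider interval, because few verified false negatives carry the weights.

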6.4.2. Intraprocedure

For safety reasons, the investigator may have the subject quit during the procedure. For example, the patient is not suitable for receiving the instrument for the study or the endoscopists do not use the specified instrument for any reason. If the following serious cases occur, please withdraw during the operation:

- 1) Perforation
- 2) Bleeding
- 3) Allergy to narcotic drugs
- 4) The anatomical structure of the upper gastrointestinal tract is abnormal and the endoscopist cannot enter the scope smoothly
- 5) Inability to complete ultrasound endoscopy due to obstruction, intolerance, etc.
- 6) Unable to complete colonoscopy due to obstruction or other reasons

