7.5. Risk minimization

In this study, when the software malfunctioned, novice doctors and experts could still operate under their own judgment without affecting the routine treatment measures, and when the judgment of the two did not agree, the expert results prevailed, which greatly reduced the risk of the trial.

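### The main analysis is per-protocol with no scoring rule for an incomplete or non-AI novice sweep, so such failures can be left out of the non-inferiority comparison

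*Combined protocol and SAP*

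**What the plan says.** **Analysis sets (section 8.4).** "The main analysis will be based on the PP analysis set", and "FAS analysis was regarded as supportive analysis". The PP set "will include all subjects in the FAS analysis set with no significant deviation from the program"; what makes a deviation significant is not defined. The FAS "will contain all eligible cases and shedding cases, but does not include culling cases"; culling is not defined either. The same section says "Intention-to-treat and conformity analysis sets should be used to analyze the primary efficacy endpoints", without defining an intention-to-treat set apart from the FAS and without saying that the two results must agree.

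**Withdrawal during the procedure (section 6.4.2).** The investigator may stop a subject for safety, one example being that "the endoscopists do not use the specified instrument for any reason". The list of events that call for withdrawal includes abnormal upper gastrointestinal anatomy such that "the endoscopist cannot enter the scope smoothly", and EUS that cannot be completed, with obstruction and intolerance given as examples in an open-ended list.

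**Malfunction (section 7.5).** "when the software malfunctioned, novice doctors and experts could still operate under their own judgment".

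**Related text.** Section 6.4 keeps results gathered up to the point of discontinuation but does not say in which analysis set. Section 6.4.3 bars replacement. Section 4.1 classifies a sweep only by whether EUS detected a stone. Section 8.2 compares categorical variables with McNemar's test, which needs a result from both readers.

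**The concern.** The usual argument for a PP analysis in a non-inferiority trial is that non-adherence blurs a real difference between arms. That argument is weaker here. Each patient is swept by both readers, and some reasons for losing a patient may be part of what is being tested: a novice who cannot finish the sweep, or software that does not work.

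There is reason to expect unequal losses. Section 3 defines a novice as having fewer than 25 independent EUS cases and an expert as having at least 3 years of EUS experience. By the study process in section 1, only the novice sweep uses the AI, and section 7.4 describes the trial instrument as software. Non-use of the device can then arise only on the novice side.

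If a patient with a failed novice sweep and a correct expert sweep drops out of the main analysis, a result that counts against the novice disappears. The FAS would be the natural check, but it is only supportive and has its own undefined exclusion.

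**Working it through.** **1. The plan's own figures.** Section 8.3 gives 147 evaluable patients and 20% loss: 147 / (1 - 0.20) = 183.75, rounded up to 184. This reproduces, and it allows 184 - 147 = 37 patients to be lost. The 147 itself cannot be confirmed, because no margin or discordance rate is stated. Several unstated pairs fit: for example, the paired formula n = psi x (z_a + z_b)^2 / margin^2 at one-sided 2.5% and 80% power gives 148 for an 8-point margin with 12% discordance, and 147 for a 10-point margin with 18.7%.

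**2. How few cases matter.** Assumptions not in the documents: 147 PP pairs, both readers 90% accurate, discordance 10% to 18%, and k excluded novice-only failures added back as incorrect for the novice, with the expert correct in 90% of them. The difference (novice plus AI minus expert) is -0.9k / (147 + k).

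| k | Difference (points) | Lower 95% limit (points) |
|---|---|---|
| 0 | 0.0 | -5.1 to -6.9 |
| 3 | -1.8 | -7.2 to -8.9 |
| 5 | -4.5/152 = -3.0 | -8.6 to -10.1 |
| 7 | -6.3/154 = -4.1 | -9.9 to -11.3 |
| 10 | -9/157 = -5.7 | -11.7 to -13.1 |

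With an assumed 10-point margin, about 5 to 8 such exclusions turn a non-inferior PP result into a failure.

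**3. False non-inferiority rate.** Assumptions: a 10-point margin, a true difference exactly at it, 4% of pairs right for the novice only, 14% right for the expert only, n = 147, and a Wald 95% interval. If a share f_n of patients is lost from the 14% cell and f_e from the 4% cell, the difference among those left is

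[(0.04 - f_e) - (0.14 - f_n)] / (1 - f_n - f_e).

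The rates come from multinomial simulation with at least 200,000 replicates per scenario.

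| Scenario | Difference among those left | False non-inferiority |
|---|---|---|
| No losses | -0.10 | about 3% |
| Equal losses, e.g. 2% each | -0.10/0.96 = -0.104 | about 3% |
| 2% novice, 1% expert | -0.09/0.97 = -0.093 | about 5% |
| 3% novice failures, pairs deleted only in group B (1.5%) | -0.085/0.985 = -0.086 | about 7% |
| 5% novice failures, group B only (2.5%) | -0.075/0.975 = -0.077 | about 12% |
| 3% novice only, both orders | -0.07/0.97 = -0.072 | about 15% |
| 5% novice only, both orders | -0.05/0.95 = -0.053 | about 36% |

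The group B rows reflect the tandem order. In group A the novice goes first, so a patient withdrawn during that sweep may never have an expert result to delete. The last two rows are the worst case: every lost pair is one in which the novice failed and the expert was right.

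**The case against.** A reader might infer more than the documents support, in five ways.

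- **That these failures are removed.** No section says that a 6.4.2 withdrawal is a significant deviation or leaves the PP set, and section 6.4 keeps results obtained before discontinuation. The text supports only that they can be removed. Keeping one reader's result does not supply the pair that McNemar's test needs, so the gap remains.
- **That the exclusions run one way.** Section 6.4.2 refers to either endoscopist. Intolerance, bleeding, perforation and drug allergy can occur in either sweep. The documents give no failure rate for either reader, and with equal rates the error stays near 3%.
- **That the scope-entry item describes novice failure.** It is conditional on abnormal anatomy, which is a feature of the patient, and section 3.2 already excludes much of it. The item on incomplete EUS is the more relevant one, though its named examples are also patient-level.
- **That 6.4.2 and 7.5 contradict each other.** The instrument clause in 6.4.2 is permissive and does not mention malfunction; 7.5 says that readers could continue. Both can stand. They are unreconciled, because neither says how such a case is classified for PP.
- **That a PP analysis is wrong in itself.** It has a recognised place in non-inferiority trials, and section 8.4 already asks for both sets on the primary endpoint.

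All five limits stand. What they leave is that undefined terms decide who is in the main analysis, and that an incomplete sweep has no score.

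**Conclusion.** The point holds in conditional form. PP is the main analysis, the FAS is only supportive, and nothing says how an incomplete or non-AI novice sweep counts. Failures of the strategy under test can therefore leave the main comparison, and the decision could be taken after results are known.

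The bias toward non-inferiority depends on novices failing more often than experts, or on device failure. Under the assumed 10-point margin and 4%/14% discordance, the false non-inferiority rate ranges from about 3% (equal failure) through 5% to 12% (modest imbalance, or losses only when the expert goes first) to between 15% and 36% (one-way losses of 3% to 5%). The upper figures are a bound, not an expectation. Without a stated margin or any failure rates, no single figure can be attached to this trial.

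**What to change.** Amend section 8.4 as follows.

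1. Claim non-inferiority only if the FAS and PP analyses agree.
2. Define the FAS as all randomised patients with at least one sweep started, and define significant deviation, shedding and culling.
3. In the FAS, keep a novice sweep done without AI after a malfunction in the novice-plus-AI result.
4. In the FAS, score a sweep not completed for a reader- or device-related reason as incorrect for that reader, in both randomised orders. State how the pair is handled when the other reader's sweep never began.
5. Add a sensitivity analysis that also counts patient-related incompletions, such as intolerance, as incorrect. Keeping these out of the main rule avoids charging the second reader for an effect of order.
6. Report incomplete sweeps by reader and by order.
7. State how 6.4.2 withdrawals and 7.5 malfunctions are classified for PP, so that the two sections are reconciled.

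The cost is SAP wording, plus recording the reason for each incomplete sweep. Both analysis sets are already planned. The downside is a slightly harder success criterion.
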